Appendix A: The Xerostomia Inventory (Thomson 1999)

1. I sip liquids to aid in swallowing food	1 Never	2 Hardly ever	3 Occasionally	4 Fairly often	5 Very often
2. My mouth feels dry when eating a meal	1 Never	2 Hardly ever	3 Occasionally	4 Fairly often	5 Very often
3. I get up at night to drink	1 Never	2 Hardly ever	3 Occasionally	4 Fairly often	5 Very often
4. My mouth feels dry	1 Never	2 Hardly ever	3 Occasionally	4 Fairly often	5 Very often
5. I have difficulty in eating dry foods	1 Never	2 Hardly ever	3 Occasionally	4 Fairly often	5 Very often
6. I suck sweets or cough lollies to relieve dry mouth	1 Never	2 Hardly ever	3 Occasionally	4 Fairly often	5 Very often
7. I have difficulties swallowing certain foods	1 Never	2 Hardly ever	3 Occasionally	4 Fairly often	5 Very often
8. The skin on my face feels dry	1 Never	2 Hardly ever	3 Occasionally	4 Fairly often	5 Very often
9. The skin on my face feels dry	1 Never	2 Hardly ever	3 Occasionally	4 Fairly often	5 Very often
10. My lips feel dry	1 Never	2 Hardly ever	3 Occasionally	4 Fairly often	5 Very often
11. The inside of my nose feels dry	1 Never	2 Hardly ever	3 Occasionally	4 Fairly often	5 Very often

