- the decrease of saliva flow rates (compared to baseline prior to definitive treatment) during radiotherapy treatment at 3, 6 weeks and prior to everolimus administration and the subsequent recovery of saliva flow rates at completion of the 5 day everolimus course and 1, 3 and 6 months after RT/chemoRT completion to determine the kinetics and stability of saliva flow rate recovery.
- protein composition within the saliva will be measured and will be expressed as percent decrease and recovery of amylase at all available time points.

- Xerostomia Visual Analog Scale survey and Xerostomia Inventory survey will be obtained from each participant at all available time points (See Appendix A and B).

4 Study design

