Sexually active males must use a condom during intercourse while taking the drug and for 8 weeks after stopping treatment and should not father a child in this period.

A condom is required to be used also by vasectomised men in order to prevent delivery of the drug via seminal fluid.

Female partners of male patients must also be advised to use one of the following contraception methods: Use of (1) oral, injected, implanted or other hormonal methods of contraception, or (2) intrauterine device (IUD) or intrauterine system (IUS), or (3) prior male/female sterilization.

Fertility

The potential for everolimus to cause infertility in male and female patients is unknown. However, menstrual irregularities, secondary amenorrhea and associated luteinizing hormone (LH)/follicle stimulating hormone (FSH) imbalance has been observed.

Based on non-clinical findings, male and female fertility may be compromised by treatment with everolimus.

7.2.2

CORRELATIVES:

The decrease of saliva flow rates (compared to baseline prior to definitive treatment) during radiotherapy treatment at 3, 6 weeks and prior to everolimus administration and the subsequent recovery of saliva flow rates at completion of the 5 day everolimus course and 1, 3 and 6 months after RT/chemoRT completion to determine the kinetics and stability of saliva flow rate recovery.

The production of the saliva protein amylase also decreases with salivary gland dysfunction following irradiation. Hence, we will measure protein composition within the saliva on an Experion microfluidic chip as previously described by the [name] lab (Grundmann 2010, Morgan-Bathke 2014, Hill 2014).). Briefly, a small amount of saliva (1-2 µl) will be loaded on the Experion microfluidic chips according to manufacturer's instructions. Sample analysis will focus on the profile and concentration of all proteins present in saliva. Percent decrease and recovery of amylase will be measured at all available time points and confirmed using immunoblotting techniques.

Surveys that will administered include:

- a. Xerostomia Inventory survey (Thomson 1999, appendix A)
- b. Xerostomia Visual Analog Scale survey (Pai 2001, appendix B)

8 Safety monitoring and reporting

Information about all adverse events, whether volunteered by the subject, discovered by investigator questioning, or detected through physical examination, laboratory test or other means, will be collected and recorded and followed as appropriate.

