As a result of these possibilities, total number of patients included in this phase 0, proof of principle trial can range from a minimum of 10 to a maximum of 16 total patients.

Maximum number of 16 patients will occur if a DLT occurs in one of the first 3 patients in the 5 mg cohort, and no DLT occurs in the additional 3 expanded cohort patients (for a total of 6 patients in the 5 mg cohort). Subsequently, 10 additional patients will be enrolled in the 10 mg cohort, for a maximum total of 16 patients.

Planned analyses will be performed by strata (patients enrolled at the 5 mg dose level versus the 10 mg dose level).

Statistical analysis will compute the mean percent recovery of all treated patients (with a 95% confidence interval). Ten patients at the selected dose will allow estimating the mean percent recovery with standard error that is 0.32 of the observed standard deviation. Exploratory analysis will determine if any clinical factors are predictive of treatment response, specifically ipsilateral vs bilateral neck irradiation. Changes in the secondary endpoints across time, including the saliva flow rates, saliva protein composition, total score obtained on the Xerostomia Inventory survey, and total score on the Xerostomia Visual Analog Scale survey, will be explored using graphical methods.

10 Protocol amendments, or changes in study conduct

Any change or addition (excluding administrative) to this protocol requires a written protocol amendment that must be reviewed by Novartis and the investigator before implementation. Amendments significantly affecting the safety of subjects, the scope of the investigation or the scientific quality of the study require additional approval by the IRB at each study center. A copy of the written approval of the IRB must be provided to Novartis. Examples of amendments requiring such approval are:

1. increases in drug dose or duration of exposure of subjects,
2. significant changes in the study design (e.g. addition or deletion of a control group),
3. increases in the number of invasive procedures,
4. addition or deletions of a test procedure required for monitoring of safety.

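### Appendix A prints the same question as items 8 and 9, so the Xerostomia Inventory total counts facial skin dryness twice

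*Protocol*

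**What the plan says.** Appendix A sets out the Xerostomia Inventory as a form with rows numbered 1 to 11. Each row has the same five answers, from 1 (never) to 5 (very often). Two adjacent rows carry the same question:

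- "8. The skin on my face feels dry"
- "9. The skin on my face feels dry"

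The other nine rows all differ from each other and from these two. The numbering has no gap and ends at "11. The inside of my nose feels dry".

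The form is in active use in the plan. Section 3 lists it among the secondary endpoints: "Xerostomia Visual Analog Scale survey and Xerostomia Inventory survey will be obtained from each participant at all available time points". Section 7.2.2 identifies the survey as the one in the appendix: "Xerostomia Inventory survey (Thomson 1999, appendix A". Table 7-1 schedules the correlative studies, of which the surveys are part, at all eight visits. Section 9.1 names the "total score obtained on the Xerostomia Inventory survey" among the secondary measures whose changes over time will be explored by graphs.

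The protocol contains no scoring rule that omits a row, no second list of the items and no correction of the form.

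**The concern.** A total score takes its meaning from the items in it. If the form is used as printed and its rows are simply added, one symptom enters twice. That symptom concerns facial skin, not the mouth, whereas the trial is about recovery of salivary function. Section 8.1.1 also lists dry skin as a common adverse reaction to everolimus. Five days of dosing may well not produce it, and Section 4.1 expects the known toxicities not to develop. Even so, the doubled item is one that could move for reasons unrelated to saliva.

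Two things are at stake. The first is how the plotted totals are read, since part of any movement may reflect facial skin at double weight. The second is comparability with scores from the cited inventory, if the repeated row stands where a different question belongs. In that case the loss cannot be repaired at analysis, because an answer to a question that was never asked cannot be recovered. With 10 to 16 patients in all, even a few visits recorded on a faulty form would be a noticeable share of the data.

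**Working it through.** The protocol states no score range, item weight or item count for this survey, so there is no figure of its own to reproduce on this point. Its only precision figure concerns the primary endpoint: "Ten patients at the selected dose will allow estimating the mean percent recovery with standard error that is 0.32 of the observed standard deviation". That is 1/√10 = 0.316, which rounds to the stated 0.32. It does not depend on the survey.

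**Inputs, all from Appendix A**

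- Numbered rows: 11
- Distinct question texts, by comparing the 11 rows: 10 (rows 8 and 9 are identical, all others are different)
- Response scale per row: 1 to 5, a span of 5 − 1 = 4 points

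**Assumption.** The total in Section 9.1 is the unweighted sum of the rows. The protocol does not say otherwise.

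**Form as printed**

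- Range: 11 × 1 = 11 to 11 × 5 = 55
- Span: 55 − 11 = 44 points
- Facial skin dryness: 2 rows × 4 = 8 points
- Share of the total: 8/44 = 2/11 = 18.2%

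**What a single row would carry.** There are two possibilities, and the documents do not decide between them.

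| Situation | Items | Range | Span | Facial skin, points | Share |
|---|---|---|---|---|---|
| As printed | 11 rows, 10 distinct | 11–55 | 44 | 8 | 18.2% |
| Row 9 took the place of another item | 11 distinct | 11–55 | 44 | 4 | 1/11 = 9.1% |
| Row 9 is surplus | 10 distinct | 10–50 | 40 | 4 | 1/10 = 10% |

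Facial skin therefore carries 18.2% of the printed total where one row would carry 9.1% or 10%. The 8 points are the extreme case, a patient who moves from never to very often on that symptom, if both rows are answered alike. A one-step change would move the total by 2 points instead of 1. The protocol gives no data from which to estimate a typical change.

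**The case against.** **The repetition may not be in the protocol itself.** Converting a PDF table to text can repeat the wording of one row under the number of the next. Unbroken numbering does not rule this out, and the weak-inhibitor list in Table 6-7 also shows repeated entries whose origin cannot be determined. This stands as a limit on certainty. A typing error in the appendix is at least as plausible, so the first step is to look at the original page. It is also possible that the sites use a correct form and only the appendix is wrong.

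**The published inventory is not in the documents.** A reader might infer that one of 11 original items was overwritten, that the proper weight is 9.1%, and that patients are not receiving the cited instrument. The protocol does not support that. It never states how many items the inventory has and does not reproduce it elsewhere. All it shows is that one question appears twice. This objection stands in full, and it is why both single-row weights are given above.

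**Little depends on this score.** Section 9.1 plans only graphical exploration of it. No test, threshold, responder definition or decision uses it. Patients serve as their own controls and, if the same form is used throughout, within-patient trends stay readable. The eight-question visual analogue survey in Appendix B is collected at the same time points, so patient-reported dryness does not rest on this form alone. No comparison with published scores is planned, and the later randomized trial is only envisaged if this one succeeds. All of this stands and keeps the point small. It does not remove the double counting.

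**A corrected sum may still not be comparable.** If an item is missing, a ten-item sum cannot be set beside totals from the published instrument. That is also right, and any report should say so.

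**Conclusion.** The point holds in a limited form. As printed, Appendix A asks the same question twice, its 11 rows hold 10 distinct questions, and a simple total counts facial skin dryness twice: 18.2% of the score and up to 8 of 44 points. No scoring rule in the protocol prevents this.

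The conclusion rests on three assumptions: the printed appendix really contains the repeat, the form is administered as printed, and the total is an unweighted sum. Whether an item was displaced or a row was added cannot be settled from the protocol.

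The consequence is confined to one descriptive secondary endpoint, where trends within patients remain readable but over-weight facial skin. It would be wrong to infer any effect on the saliva-flow primary endpoint, the sample size or the dose-escalation rule, since none of them uses the survey. The correction is worth making because it costs so little and because answers to a missing question, if there is one, cannot be obtained later.

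**What to change.** 1. Check the original Appendix A page, and the form in use at both sites, against the cited inventory.
2. If the duplicate is confirmed, correct row 9: restore the displaced item if there is one, or delete the row if it is surplus. Re-issue the form to both sites. If only the appendix is wrong, correct the appendix.
3. For visits already recorded on the duplicated form, report the sum with facial skin counted once. That gives ten items with a range of 10 to 50. Where a patient's answers to rows 8 and 9 differ, fix in advance which one is used. If an item is missing, state that this sum is not comparable with totals from the published instrument.

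The cost is one row on a questionnaire, a re-issued form, and whatever amendment step Section 10 requires. Sample size, visit schedule and the primary analysis do not change.

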Appendix B: Visual Analog Scale (VAS) Xerostomia Questionnaire (Pai 2001)

1. Rate the difficulty you experience in speaking due to dryness

Not difficult at all Very difficult

2. Rate the difficulty you experience swallowing due to dryness

Not difficult at all Very difficult

3. Rate how much saliva is in your mouth

A lot None

4. Rate the dryness of your mouth

Not dry at all Very dry

5. Rate the dryness of your throat

Not dry at all Very dry

6. Rate the dryness of your lips

Not dry at all Very dry

7. Rate the dryness of your tongue

Not dry at all Very dry

8. Rate the level of your thirst

Not thirsty at all Very thirsty
